Appendix B: Acceptable Ranges of Screening Laboratory and Vital Sign Measurements

Table 4: Acceptable Ranges of Screening Laboratory and Vital Sign Measurements – Hematology and Chemistry

HEMATOLOGY AND CHEMISTRY				
Lab test name	Reference range	Acceptable lower limit	Acceptable upper limit	Lab unit
Hemoglobin (Hgb), male	13.2 - 17.1	13.0	18.5	g/dL
Hemoglobin (Hgb), female	11.7 – 15.5	11.3	16.5	g/dL
Hematocrit (Hct), male	38.5 – 50.0	38.5	54	%
Hematocrit (Hct), female	35 - 45	35	49	%
White blood cell count (WBC)	3,800 – 10,800	3,500	11,500	cells/ μ L
Neutrophil count	1,500 – 7,800	1,200	8,500	cells/ μ L
Lymphocyte count	850 – 3,900	800	5,000	cells/ μ L
Monocyte count	200 - 950	0	1,100	cells/ μ L
Eosinophil count	150 - 500	0	600	cells/ μ L
Basophil count	0-200	0	300	cells/ μ L
Platelet count	140 - 400	125	475	$10^3/\mu$ L
Sodium	135 - 146	132	148	mmol/L
Potassium	3.5 - 5.3	3.3	5.5	mmol/L
CO ₂ (Bicarbonate)	20 - 32	19	33	mmol/L
Chloride	98 -110	94	115	mmol/L
Calcium	8.6 - 10.3	8.0	11.0	mg/dL
Magnesium	1.5 - 2.5	1.1	2.8	mg/dL
Blood urea nitrogen (BUN)	7 – 25	0	28	mg/dL
Glucose, fasting	65 - 99	50	115	mg/dL
Serum creatinine, male	0.6 – 1.35	0.5	1.45	mg/dL
Serum creatinine, female	0.5 – 1.10	0.4	1.2	mg/dL
Direct bilirubin	0.0-0.2	0	0.4	mg/dL
Total bilirubin	0.2 – 1.2	0	1.4	mg/dL
Total protein	6.1 - 8.1	5.8	8.6	g/dL
Albumin	3.6 – 5.1	3.2	6.0	g/dL
Aspartate transferase (AST), male	10 - 40	0	45	U/L
Aspartate transferase (AST), female	10 - 30	0	35	U/L
Alanine transferase (ALT), male	9 - 46	0	52	U/L
Alanine transferase (ALT), female	5 - 32	0	38	U/L
Alkaline phosphatase, males	40 - 115	0	150	U/L
Alkaline phosphatase, females	33 – 115	0	150	U/L
Hepatitis B surface antigen (HBsAg)	non-reactive	non-reactive	non-reactive	n/a
Hepatitis C antibody (HCVAb)	non-reactive	non-reactive	non-reactive	n/as
HIV-1/ HIV-2 antibody	non-reactive	non-reactive	non-reactive	n/a

Serum β -HCG (females only)	negative	negative	negative	n/a
FSH (post-menopausal females only)	23 – 116.3	23	116.3	mIU/mL

Footnotes: Exceptions to screening laboratory tests' normal reference ranges are:

- a. Racially-based low total WBC or neutrophil counts up to toxicity Grade 1 in [Appendix C](#) Toxicity Tables are allowed, but toxicity Grades 2 or 3 are exclusionary.

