- b. Abnormalities in mean corpuscular volume (MCV), mean corpuscular hemoglobin (MCH), mean corpuscular hemoglobin concentration (MCHC), red cell distribution width (RDW), mean platelet volume (MPV), and nucleated red blood cell count (NRBC CT), which are included in a CBC with differential, will not be exclusionary. These results will be included in the database for comparison with results obtained as a part of safety laboratory tests.
- c. Abnormalities in serum creatinine, BUN, total bilirubin, AST, ALT, and chloride below the lower limit of normal (LLN) are allowable.
- d. Elevated bilirubin due to documented Gilbert syndrome that is Grade 1 is allowable, but Grade 2 or higher is exclusionary. [To document a subject has Gilbert syndrome, a diagnosis from the medical record must will be provided or the PI may make a 'presumptive' diagnosis of Gilbert syndrome in subjects with unconjugated hyperbilirubinemia on repeated testing (at least two samples separated in time) who have otherwise normal serum ALT, AST, and AP concentrations, and a normal CBC].
- e. Elevated serum glucose, sodium, potassium, bicarbonate (CO₂), total protein, and AP values that reach toxicity Grade 1 values are allowable.
- f. Serum chloride and albumin values above the ULN are allowable.
- g. Other laboratory values that are outside the range of eligibility but are thought to be due to an acute condition or due to collection or laboratory error may be repeated once.

URINALYSIS ^a

Table 5: Acceptable Ranges of Screening Laboratory and Vital Sign Measurements – Urinalysis

Lab test name	Reference range limit	Acceptable lower limit	Acceptable upper limit	Lab unit
Urine dipstick				
Protein	negative	negative	1+ ^b	
Blood	negative	negative	trace ^b	
Glucose	negative	negative	trace ^b	
Urine Microscopy				
WBCs in urine (sediment)	0-5	0	6	/field
RBCs in urine (sediment)	0-2	0	6	/field
Bacteria	none	few	^b	/field
Hyaline casts	none	none	trace ^b	/field
Crystals	none	0	^b	
Footnotes:				
^a (1) If UA by dipstick is abnormal, a complete UA with microscopic evaluation will be performed and the results will supersede the results of the dipstick. (2) Menstruating females failing inclusion criteria due to a positive blood on a urine test (dipstick or microscopic UA) may be retested following cessation of menses. Do not exclude female subjects with ≤ 6 RBC/HPF.				
^b Per investigator judgment, based on medical history.				

TOXICOLOGY

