Mucocutaneous	Erythema, pruritus	Diffuse, maculopapular rash, dry desquamation	Vesiculation OR moist desquamation OR ulceration	
Pruritus	No or minimal interference with usual social and functional activities	Greater than minimal interference with usual social and functional activities	Inability to perform usual social and functional daily activities	
ALL OTHER CONDITIONS				
Illness or clinical AE (as defined according to applicable regulations)	Require minimal or no treatment; does not interfere with the subject's daily activities.	Result in a low level of inconvenience or concern with therapeutic measures; may cause some interference with functioning.	Interrupt a subject's usual daily activity and may require systemic drug therapy or other treatment; are usually incapacitating	

Table 8: Toxicity Grading Tables – Laboratory AEs

Laboratory AEs	Mild (Grade 1)	Moderate (Grade 2)	Severe (Grade 3)
Blood, serum, or plasma *			
Sodium decrease – mmol/L	130 - 131	125 –129	<125
Sodium increase – mmol/L	149 - 150	151 – 153	>153
Potassium increase – mmol/L	5.6 – 6.0	6.1 – 6.4	≥6.5
Potassium decrease – mmol/L	3.0 – 3.2	2.5 – 2.9	<2.5
Bicarbonate (CO ₂) increase – mmol/L	34 - 35	36 - 37	>37
Bicarbonate (CO ₂) decrease – mmol/L	17 - 18	14 - 16	<14
Glucose decrease, fasting – mg/dL	47 - 49	45 –46	<45
Glucose increase, fasting – mg/dL	116 – 125	126 – 249	≥250
Glucose increase, non-fasting – mg/dL	116 – 160	161 – 249	≥250
Blood urea nitrogen – mg/dL	25 - 27	28 – 32	>32
Creatinine increase, male – mg/dL	1.46 – 1.7	1.71 – 2.3	>2.3
Creatinine increase, female – mg/dL	1.21 – 1.5	1.51 – 2.0	>2.0
Calcium decrease – mg/dL	7.8 – 8.0	7.0 – 7.7	<7.0
Calcium increase – mg/dL	11.0 – 11.4	11.5 – 12.4	≥12.5
Total protein decrease – g/dL	5.1 – 5.7	4.6 – 5.0	<4.6
Albumin decrease – g/dL	2.8 – 3.4	2.5 – 2.7	<2.5
AST increase, male – U/L	46 – 115	116 – 220	>220
AST increase, female – U/L	36 - 90	91 - 175	>175
ALT increase, male – U/L	53 – 115	116 - 230	>230
ALT increase, female – U/L	39 – 95	96 – 190	>190
Alkaline phosphatase increase – U/L	151 – 240	241 – 360	>360
Total bilirubin (serum) increase – mg/dL (with other LFTs in the normal range)	1.5 – 2.0	2.1 – 2.5	>2.5
Total bilirubin (serum) increase – mg/dL (accompanied by a >3 x ULN increase in ALT or AST)**	1.5 – 1.7	1.8 – 2.1	>2.1
Hemoglobin decrease, female – g/dL	10.8 – 11.2	9.4 – 10.7	<9.4
Hemoglobin decrease, male – g/dL	11.8 – 12.9	10.0 – 11.7	<10.0
WBC increase – cells/μL	11,000 – 15,000	15,001 – 20,000	>20,000

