WBC decrease – cells/μL	2,500 – 3,500	1,500 – 2,499	<1,500
Neutrophils decrease – cells/μL	1,200 – 1,499	1,000 – 1,199	<1,000
Lymphocytes decrease – cells/μL	750 – 849	500 – 749	<500

Laboratory AEs	Mild (Grade 1)	Moderate (Grade 2)	Severe (Grade 3)
Monocytes increase – cells/μL	1,101 – 2,000	2,001 – 3000	>3,000
Eosinophils increase – cells/μL	500 – 750	751 – 1,500	>1,500
Basophils increase – cells/μL	201 – 500	501 – 800	>800
Platelets decrease – cells/μL	120,000 – 124,000	100,000 – 119,000	<100,000
Urine*			
Protein	1+	2+	>2+
Glucose	1+	2+	>2+
Blood (dipstick)	1+	2+	>2+
Blood (microscopic) – RBCs per HPF	6-10	11-50	>50 and/or gross blood
WBC (microscopic) – WBC per HPF	6-10	11-50	>50
Bacteria (microscopic)	few	moderate	many

* Institutional normal reference ranges and allowable ranges at screening are provided in [Appendix B](#).

**ALT, males: >216 U/mL; ALT, females: >132 U/mL; AST, male or female: >126 U/mL)

Note 1: If a subject was accepted into the trial with a laboratory value of an analyte that overlaps with values used for grading Grade 1 laboratory abnormalities, an AE will be reported if the on-study value of the same analyte is different (worse) from the baseline.

Note 2: Safety laboratory results that are abnormal according to the local laboratory reference range, but not considered a Grade 1 abnormality, will be evaluated by the CTU clinician and reported as Grade 1 abnormalities if clinically significant. If not clinically significant, these will not be considered laboratory AEs and will thus not be graded but will be recorded in the source document and followed-up clinically at the discretion of the CTU clinician.

Note 3: Other laboratory parameters performed and reported as part of the CBC, metabolic panel, and UA will be evaluated by the study clinician, recorded in the source document, reported as laboratory AEs if clinically significant, and graded according to the criteria in [Section 9.2.1](#).

Note 4: If the dipstick UA is abnormal, a microscopic UA will be performed, and the results will supersede the results of the dipstick UA.

Note 5: Menstruating females with a positive dipstick UA or microscopic UA may be retested following cessation of menses.

Table 9: Toxicity Grading Tables – ECG

ECG interval abnormality	Grade 1	Grade 2	Grade 3

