9. SAFETY EVALUATION

All safety analyses will be presented using the safety population. Subjects will be grouped for summary statistics by Treatment, as defined in Section 3.3.

When calculating the incidence of AEs (i.e., on a per subject basis), each subject will be counted once and any repetitions of unsolicited AEs within a subject (by treatment) will be ignored for events coded in the same category by the Medical Dictionary for Regulatory Activities (MedDRA®). The denominators for percent values will be indicated within the table or table header and denominators will consist of the maximal size of the safety population in the indicated observation period. Moreover, events thus summarized will be coded to the highest severity observed. If the time interval defined by the start date and end date of the AE overlaps more than 1 period, the AE will be associated with treatment immediately preceding the AE start date only, and the AE will be graded according to the maximum severity of the event at any time prior to the AE end date. Abnormal laboratory values or clinical findings measured after dosing will be reported using the toxicity scales in [Table 3](#) and [Table 4](#).

All laboratory, vital signs, and ECG results obtained after the first dose that have programmable criteria described in the toxicity scales will be graded for the CSR according to the programmable criteria, and toxicity grades of mild, moderate, or severe will be indicated for the result in the listings. For criteria involving a change from baseline, the baseline to be used is described in Section 3.3.

If a subject was accepted into the trial with a laboratory, vital signs, or ECG parameter value that overlaps with values used for grading Grade 1 laboratory abnormalities, the result will only be graded (mild or worse) if the post-dose measurement of the parameter is different (worse) than baseline. In other words, a result will be graded as mild, moderate, or severe if and only if it both meets the grading criteria in [Table 3](#) or [Table 4](#) and is worse than baseline by any amount.

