Only laboratory parameters reported as continuous values will be included in tables of summary statistics for change from baseline and in box plots for change from baseline. Because microscopic urinalysis evaluation is only performed in subjects with an abnormal urine dipstick result, urinalysis parameters assessed by microscopic evaluation will be excluded from tables of summary statistics for change from baseline and in box plots for change from baseline. However, urinalysis parameters assessed by microscopic evaluation will be included in summaries of toxicity grading, where the toxicity grade will be imputed as “Normal” for subjects where microscopic evaluation was not performed.

Laboratory parameters that have grading criteria for both decreases (result lower than normal range and baseline measurement) and increases (result higher than normal range and baseline measurement) will be summarized separately by direction of change. For example, sodium will be summarized separately as “Sodium, Decrease” and “Sodium, Increase.”

In tables summarizing toxicity grading, maximum severity observed for the parameter after dosing and within the same dosing period will be summarized (max severity post-baseline). Results of maximum severity for “Any Parameter” will be included for chemistry, hematology, and urinalysis laboratory results. For “Any Parameter” results, the maximum severity across all laboratory parameters in the respective category is summarized by time point, and from maximum severity post baseline.

By protocol, up to one repeat of a planned clinical laboratory assessment is allowed (*Laboratory values that are outside the range of eligibility but are thought to be due to an acute condition or due to collection or laboratory error may be repeated once.*). If replicates for clinical laboratory results are present in the database, then only the second replicate will be summarized and reported. Replicates not used in the analysis will not be listed.

Viral serology screening results ([Listing 12](#)), urine toxicology and alcohol screening results ([Listing 13](#)), and serum hCG (Human Chorionic Gonadotropin) pregnancy test results ([Listing 14](#)) will be listed. If FSH is measured for any subject during the study, FSH will be included in [Listing 14](#).

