12.4.1 Individual Laboratory Measurements and Abnormal Laboratory Values**Table 4: Laboratory Adverse Event Grading Scale**

Laboratory AEs	Mild (Grade 1)	Moderate (Grade 2)	Severe (Grade 3)
Chemistry			
Sodium decrease – mmol/L	130 - 131	125 –129	<125
Sodium increase – mmol/L	149 - 150	151 – 153	>153
Potassium increase – mmol/L	5.6 – 6.0	6.1 – 6.4	≥6.5
Potassium decrease – mmol/L	3.0 – 3.2	2.5 – 2.9	<2.5
Bicarbonate (CO ₂) increase – mmol/L	34 – 35	36 – 37	>37
Bicarbonate (CO ₂) decrease – mmol/L	17 - 18	14 - 16	<14
Glucose decrease, fasting – mg/dL	47 - 49	45 –46	<45
Glucose increase, fasting – mg/dL	116 – 125	126 – 249	≥250
Glucose increase, non-fasting – mg/dL	116 – 160	161 – 249	≥250
Blood urea nitrogen – mg/dL	25 - 27	28 – 32	>32
Creatinine increase, male – mg/dL	1.46 – 1.70	1.71 – 2.30	>2.30
Creatinine increase, female – mg/dL	1.21 – 1.50	1.51 – 2.00	>2.00
Calcium decrease – mg/dL	7.8 – 8.0	7.0 – 7.7	<7.0
Calcium increase – mg/dL	11.0 – 11.4	11.5 – 12.4	≥12.5
Total protein decrease – g/dL	5.1 – 5.7	4.6 – 5.0	<4.6
Albumin decrease – g/dL	2.8 – 3.4	2.5 – 2.7	<2.5
AST increase, male – U/L	46 – 115	116 – 220	>220
AST increase, female – U/L	36 - 90	91 - 175	>175
ALT increase, male – U/L	53 – 115	116 - 230	>230
ALT increase, female – U/L	39 – 95	96 – 190	>190
Alkaline phosphatase increase – U/L	151 – 240	241 – 360	>360
Total bilirubin (serum) increase – mg/dL (with other LFTs in the normal range)	1.5 – 2.0	2.1 – 2.5	>2.5
Total bilirubin (serum) increase – mg/dL (accompanied by a >3 x ULN increase in ALT or AST)**	1.5 – 1.7	1.8 – 2.1	>2.1
Hematology			
Hemoglobin decrease, female – g/dL	10.8 – 11.2	9.4 – 10.7	<9.4
Hemoglobin decrease, male – g/dL	11.8 – 12.9	10.0 – 11.7	<10.0
WBC increase – cells/μL	11,000 – 15,000	15,001 – 20,000	>20,000
WBC decrease – cells/μL	2,500 – 3,500	1,500 – 2,499	<1,500
Neutrophils decrease – cells/μL	1,200 – 1,499	1,000 – 1,199	<1,000
Lymphocytes decrease – cells/μL	750 – 849	500 – 749	<500
Monocytes increase – cells/μL	1,101 – 2,000	2,001 – 3000	>3,000
Eosinophils increase – cells/μL	500 – 750	751 – 1,500	>1,500
Basophils increase – cells/μL	201 – 500	501 – 800	>800
Platelets decrease – cells/μL	120,000 – 124,000	100,000 – 119,000	<100,000

Laboratory AEs	Mild (Grade 1)	Moderate (Grade 2)	Severe (Grade 3)
Urinalysis			
Protein	1+	2+	>2+
Glucose	1+	2+	>2+
Blood (dipstick)	1+	2+	>2+
Blood (microscopic) – RBCs per HPF	6-10	11-50	>50 and/or gross blood
WBC (microscopic) – WBC per HPF	5-10	11-50	>50

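### SAP Table 4 starts microscopic urine WBC Grade 1 at 5 per HPF, a value the protocol treats as normal and leaves ungraded

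*SAP*

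**What the plan says.** Three tables bear on the urine count.

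- SAP Appendix 1, Table 4, row "WBC (microscopic) – WBC per HPF": Grade 1 is 5-10, Grade 2 is 11-50, Grade 3 is above 50.
- Protocol Appendix C, Table 8, row with the same label: Grade 1 is 6-10, with Grades 2 and 3 as in the SAP.
- Protocol Appendix B, Table 5, row beginning "WBCs in urine (sediment": reference range 0-5, acceptable at screening up to 6.

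SAP Section 9 gives the programming rule: "a result will be graded as mild, moderate, or severe if and only if it both meets the grading criteria in". The criteria meant are those of the two toxicity tables (Table 4 for laboratory results). The second condition is that the result must be worse than baseline, however small the difference. SAP Section 9.6 limits where this can apply to urine cells: "Because microscopic urinalysis evaluation is only performed in subjects with an abnormal urine dipstick result", subjects without microscopy have their toxicity grade imputed as normal. SAP Section 15 declares no change to the planned analyses, so the SAP does not explain why its threshold differs from the protocol's.

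**The concern.** A grading table in an SAP should reproduce the protocol's table or say why it does not. Here one lower bound differs by 1 per HPF, and the extra value lies inside the reference range. The Section 9 rule is mechanical, so a programmer following it would label a rise from, say, 3 to 5 per HPF as mild.

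SAP Section 9.6 sends graded results to the listings of abnormal laboratory results (Table 19 for urinalysis) and to the summary of urinalysis by severity (Table 24). A normal value would then appear among abnormal results in the study report, with a grade that an investigator using Protocol Table 8 would not have assigned. Section 9.6 also provides a separate flag for results that are outside the normal range but ungraded. This case is the reverse: a result inside the normal range that carries a grade.

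**Working it through.** The plan states no figure to reproduce. The check is a row-by-row comparison of bounds.

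**Inputs.** Grade 1 bounds come from Protocol Appendix C, Table 8 and SAP Appendix 1, Table 4. Reference ranges come from Protocol Appendix B, Tables 4 and 5. There are 34 numeric grading rows with an Appendix B range: 32 blood and 2 urine microscopy.

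**Test.** For an increase, Grade 1 overlaps normal if its lower bound is at or below the upper limit of normal (ULN). For a decrease, it overlaps if its upper bound is at or above the lower limit of normal. Separately, compare the Grade 1 band between the two documents.

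**Rows where either test is positive:**

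| Row | Reference range | Protocol Grade 1 | SAP Grade 1 | Protocol overlap | SAP overlap | Documents differ |
|---|---|---|---|---|---|---|
| Urine WBC, per HPF | 0-5 | 6-10 | 5-10 | none (6 > 5) | at 5 (5 = 5) | yes |
| BUN, mg/dL | 7-25 | 25-27 | 25-27 | at 25 | at 25 | no |
| Eosinophils, cells/µL | 150-500 | 500-750 | 500-750 | at 500 | at 500 | no |

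The BUN rows are "Blood urea nitrogen – mg/dL" in the grading tables and the row beginning "Blood urea nitrogen (BUN" in Appendix B. The eosinophil rows are "Eosinophils increase" and "Eosinophil count".

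**Counts.** Grade 1 meets the reference range in 2 of 34 protocol rows and 3 of 34 SAP rows, each time at one boundary value. Only urine WBC has a Grade 1 band that differs between the documents. In the remaining rows Grade 1 starts outside the range: for example, basophils at 201 against a ULN of 200, and lymphocytes at 849 against a lower limit of 850. Grade 2 meets the reference range in 0 of 34 rows.

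**Applying the SAP rule to urine WBC.** Take a baseline of 3 and a post-dose 5, with microscopy done.

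- SAP: 5 lies in 5-10 and 5 > 3, so the result is mild.
- Protocol: 5 < 6, so there is no grade, and 5 lies in 0-5, so the value is normal.

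**After the change.** With Grade 1 at 6-10 in the SAP, the lower bound 6 exceeds the ULN 5. The overlap is empty and the two documents agree. With BUN at 26-27 and eosinophils at 501-750, 26 > 25 and 501 > 500, so those overlaps are empty too.

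The comparison covers these numeric bounds only, not footnotes or other table content.

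**The case against.** The strongest reply is that only one of the three rows is an inconsistency. For BUN and eosinophils the SAP copies the protocol faithfully. Protocol Appendix C says that its tables were adapted from standard scales to suit the sponsor's trials, so where Grade 1 begins is the sponsor's choice. Protocol Section 9.2.3 asks for a regular amendment after a change in laboratory ranges only when a normal value would reach Grade 2. Contact with Grade 1 is therefore tolerated. This stands, and it is why the BUN and eosinophil rows are an optional remark here.

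It is also fair to say that the urine item is very narrow. It needs an abnormal dipstick, a microscopy result of exactly 5 and a lower baseline. That stands as a statement of size. It does not justify the threshold, because nothing in the SAP suggests that 5 was chosen deliberately.

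A reader might infer that adverse event counts are inflated. For urine WBC the documents do not support this: a value of 5 has no grade in Protocol Table 8, so Section 9.2.3 does not call for it to be entered as an event. For BUN 25 or eosinophils 500, Section 9.2.3 speaks of abnormalities, and whether a value inside the reference range is one is a matter of reading.

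A reader might also see an error in BUN 28, which is both the top of the acceptable entry range and the start of Grade 2. It is not one. The value 28 is above the ULN of 25, so grading it is not spurious, and Protocol Sections 8.2.1 and 9.2.3 do not count an entry value as an event unless it worsens.

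**Conclusion.** The concern holds for urine WBC: the SAP's Grade 1 threshold is wrong as written, by 1 per HPF, and would label a normal result as mild. It is minor. The reach is one value in one row, shown in the urinalysis grading tables and listings. How often it would arise cannot be estimated from the documents.

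It would be too strong to infer any effect on trial conduct or on the main result. The SAP grades are assigned for the study report. Protocol Section 7.3 allows further dosing after a Grade 1 event if the investigator sees no risk or confounding. The adverse-event halting criteria in Section 9.5.1 that depend on a grade require Grade 3. The primary QTcF analysis uses none of these tables.

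The conclusion rests on three assumptions: the laboratory reports urine WBC as a single count, the field in Appendix B is the high-power field of the grading tables, and the baseline count is below 5.

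**What to change.** In SAP Appendix 1, Table 4, change urine WBC (microscopic) Grade 1 from 5-10 to 6-10. This is a one-cell edit with no change to data collection or to the protocol.

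Optionally, start BUN Grade 1 at 26 and eosinophil Grade 1 at 501. If this is done, it should be done in both Protocol Table 8 and SAP Table 4, because changing only the SAP would create two new mismatches. That is two rows in each table. Protocol Section 14.2 requires ethics approval of amendments before use, so it is sensible only as part of an amendment made for other reasons. Leaving these two rows as they are is also acceptable.
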